## 8.0 DRUG INFORMATION

3'-deoxy-3'-[F]-fluorothymidine

**Other names for the drug(s):** F FLT

**Classification - type of agent:** Radiopharmaceutical

**Mode of action:** Fluorothymidine is an analog of the nucleoside thymidine (deoxythymidine) but the 3'-F atom prevents FLT from following the full biochemical pathway of thymidine. Once in the cell, FLT is a substrate for thymidine kinase I (TK1) and is phosphorylated but is not incorporated into DNA.

**Protocol dose:** 5 mCi (+/- 20%)

**Preparation:** Provided as unit dose by the UTSW cyclotron facility to inject into patients. FLT is administered to subjects by intravenous injection of  $\leq$  10 mL. The drug

---

solution is stored at room temperature in a gray butyl septum sealed, sterile, pyrogen-free glass vial and has an expiration time of 8 hours.

**Route of administration for this study:** intravenous

**Incompatibilities:** no known incompatibilities

**Availability:** Produced at the UT Southwestern Cyclotron facility under an FDA IND

**Side effects:**

No adverse events have been attributed to Positron-Emission Tomography (PET) imaging/diagnostic administration of [3'-deoxy-3'-[F]fluorothymidine (FLT) at the levels injected. Therefore, no adverse events are expected as a result of the intravenous (IV) administration of F FLT.

As with many intravenously administered agents, 3'-deoxy-3'-[F] fluorothymidine could cause an allergic reaction that could potentially pose a threat to life (anaphylaxis). This has not been observed in limited human exposure to date. Reasonable precautions will be taken, consistent with normal radiologic and clinical facility practice. The patient will be monitored until the PET procedure is completed, and trained personnel will be available per facility standards.

## **9.0 STATISTICAL CONSIDERATIONS**

### **9.1 Study Design/Study Endpoints**

We anticipate to enroll 20 patients with biopsy proven pancreatic adenocarcinoma that are not eligible for resection by the time of the diagnosis. These patients are going to be treated with chemotherapy only or chemoradiation in selected cases. These patients will undergo an optional F FDG PET/CT (as standard of care clinical baseline) and F-FLT PET/CT before treatment (research baseline study), and after two cycles of chemotherapy (research early therapy assessment study).

For the F-FLT PET/CT analysis, SUV max, SUV peak and proliferative tumor volume will be measured by MIMvista software and compared between the two studies. Tumor size and extension will also be evaluated on CT images from the PET/CT study.

At completion of treatment (6 months after baseline FLT PET/CT) an anatomic study (MRI or CT) will be performed as standard of care in our institution to reassess the tumor and classify it as resectable or non-resectable. Also at 6 months, 1 year and 2 years after initial baseline scan, or before if clinically indicated, standard of care anatomic study (MRI or CT) will also be performed and will be reevaluated by RECIST criteria to determine stability versus progression of disease.

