**STUDY SUMMARY**

Title	Initial evaluation of role of early interim F-FLT PET/CT for outcome prediction in pancreatic adenocarcinoma
Short Title	FLT PET/CT and Pancreatic cancer early therapy assessment
Protocol Number	Version 7
Phase	Clinical study phase (e.g., Phase II)
Methodology	Prospective cohort study
Study Duration	2 years
Study Center(s)	UT Southwestern Medical Center - Single-center
Objectives	
 
• To assess if percentage change in F-FLT PET/CT quantitative parameters (SUV max, or SUV peak or proliferative tumor volume) after 2 cycles of neoadjuvant chemotherapy can predict overall survival at 1 and 2 years and progression free survival at 6 months and 1 year in patients with resectable, borderline resectable or locally advanced pancreatic adenocarcinoma.
 

Number of Subjects	20 patients with pancreatic adenocarcinoma

Diagnosis and Main Inclusion and exclusion Criteria	
 
• Patients must be over 18 years old and capable and willing to provide informed consent
 
• Patients of childbearing potential must have a negative urine or serum pregnancy test within 7 days prior to PET/CT imaging per institution's standard of care
 
• Medically stable as judged by patient's physician
 
• Patients must have an ECOG performance status of 0-3 (restricted to ECOG PS 0-2 if age >70 years)
 
• Patients with known allergic or hypersensitivity reactions to previously administered radiopharmaceuticals of similar chemical or biologic composition to FLT are not eligible
 
• Patient must NOT be breast-feeding
 
• Histologically confirmed resectable, borderline resectable or locally advanced pancreatic adenocarcinoma 
 
• Patient have measurable disease (by RECIST 1.1 criteria)
 
 
 
• Patients with a history of prior therapy for pancreatic adenocarcinoma are NOT eligible 
 
• Patient must not weigh more than the maximum weight limit for the table for the PET/CT scanner (>200kg or 440lbs).
 
 
 
• Patient must be able to lie still for a 20 to 30 minutes for whole body PET/CT scan
 

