## **2.0 STUDY OBJECTIVES**

### **2.1 Primary Objectives**

- a. To assess if percentage change in FFLT PET/CT quantitative parameters (SUV max, or SUV peak or proliferative tumor volume) after 2 cycles of chemotherapy can predict overall survival at 1 and 2 years in patients with resectable, borderline resectable or locally advanced pancreatic adenocarcinoma.

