### **2.2 Secondary Objectives**

- b. To assess if percentage change in FFLT PET/CT quantitative parameters (SUV max, or SUV peak or proliferative tumor volume) after 2 cycles of chemotherapy can predict progression free survival at 6 months and 1 year in patients with resectable, borderline resectable or locally advanced pancreatic adenocarcinoma.

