### **2.4 Endpoints**

Primary endpoint is to determine that a positive response (decrease on quantitative parameters) at an interim F FLT PET/CT (performed after 2 cycles of chemotherapy) is related to longer progression free survival and overall survival.

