### 3.1 Inclusion Criteria

[figure not shown]
- a. Patients with histologically confirmed pancreatic adenocarcinoma (resectable, borderline resectable or locally advanced disease at presentation) are eligible for the study.
- b. Patients should not have any type of curative or palliative therapy for pancreatic adenocarcinoma before enrolling in the study and should be candidates for induction chemotherapy.
- c. Patients must be over 18 years old and capable and willing to provide informed consent.
- d. Patients must have measurable disease (by RECIST 1.1 criteria)
- e. Patients must have an ECOG performance status of 0-3 (restricted to ECOG PS 0-2 if age >70 years).
- f. Patients of childbearing potential must have a negative urine or serum pregnancy test within 7 days prior to the FLT PET/CT and the optional FDG PET/CT imaging per institution's standard of care; A female of childbearing potential is any woman (regardless of sexual orientation, having undergone a tubal ligation, or remaining celibate by choice) who meets the following criteria;
  - i. Has not undergone a hysterectomy or bilateral oophorectomy; or
  - ii. Has not been naturally postmenopausal for at least 12 consecutive months (i.e., has had menses at any time in the preceding 12 consecutive months).
- g. Medically stable as judged by patient's physician.

- h. Patients with known allergic or hypersensitivity reactions to previously administered radiopharmaceuticals of similar chemical or biologic composition to FLT or FDG are NOT eligible.
- i. Ability to understand and the willingness to sign a written informed consent.
- j. Patient must be able to lie still for a 20 to 30 minute PET/CT scan.

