## **9.3 Data Analyses Plans**

Primary outcome variable: The difference in SUVmax, SUVpeak and proliferative tumor volume between baseline and 2 cycles of chemotherapy will be correlated with overall survival at 1 and 2 years and with progression free survival at 6 months and at 1 year.

The primary outcome of the study is to establish which degree of change in the PET/CT quantitative parameters can predict patients overall survival and progression free survival. The SUVmax (representing the single voxel with the highest activity concentration), SUV peak (which is defined as the average SUV within a 1 cubic cm volume within the region of the tumor with the highest metabolic activity) and proliferative tumor volume of the pancreatic tumor will be measured.

Univariate and multiple cox regression model are going to be used. P-value less than 0.05 will be considered as statistical significant.

Secondary outcome variable: the difference in SUVmax, SUVpeak and proliferative tumor volume between baseline and 2 cycles of chemotherapy will be correlated with binary tumor outcome measured from MRI/CT (resectable versus non-resectable disease) at 6 month using logistic regression. A multiple logistic regression with stepwise selection algorithm will be used to select the most correlated variable(s). Areas under the ROC curve (AUC) and corresponding 95% confidence interval will be calculated for all models. Leave one out cross validation will be applied to avoid over-fit.

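### Section 9.1 describes a cohort not eligible for resection, but 3.1.a admits resectable disease, so the pooled 6-month resectability analysis in 9.3 cannot be read as predicting who becomes resectable

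*Combined protocol and SAP*

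**What the plan says.** Section 9.1 describes the cohort thus: "We anticipate to enroll 20 patients with biopsy proven pancreatic adenocarcinoma that are not eligible for resection by the time of the diagnosis". Other current sections describe a wider one:

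- Criterion 3.1.a: patients with "resectable, borderline resectable or locally advanced disease at presentation) are eligible for the study".
- Study Summary, main criteria: "Histologically confirmed resectable, borderline resectable or locally advanced pancreatic adenocarcinoma".
- Objective 2.1 concerns OS "in patients with resectable, borderline resectable or locally advanced pancreatic adenocarcinoma". Objective 2.2 asks whether FLT change "can predict progression free survival at 6 months and 1 year in patients with resectable, borderline resectable or locally advanced pancreatic adenocarcinoma".

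Nothing in 3.2 excludes resectable disease. Criterion 3.1.b requires candidates for induction chemotherapy, and Section 3.0 rules out eligibility waivers.

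At about 6 months, 9.1 has a CT or MRI done "to reassess the tumor and classify it as resectable or non-resectable". Section 9.3 makes this a secondary outcome: the changes in SUVmax, SUVpeak and proliferative tumor volume "will be correlated with binary tumor outcome measured from MRI/CT (resectable versus non-resectable disease) at 6 month using logistic regression", with stepwise selection, AUC and leave-one-out cross-validation. Neither section refers the 6-month status to the patient's class at baseline.

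**The concern.** The same binary outcome carries different meanings in the two cohorts. If nobody is resectable at entry, a resectable result at 6 months means the tumor became resectable. If some patients are resectable at entry, a resectable result may mean only that nothing was lost.

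Section 1.1 gives the main therapeutic goal as reducing disease so that surgery becomes possible, and 9.1 describes patients who cannot have surgery at diagnosis. A reader of the 6-month AUC will therefore naturally take it as a measure of how well early FLT change picks out patients who convert. With resectable patients pooled in, it is not that measure. It partly reflects how FLT change differs between patients who started in different classes.

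**Working it through.** **Figure in the plan.** The only related figure is the sample size in 9.2. The normal approximation reproduces it: ((1.960 + 0.842) × 0.17/0.124)² = 14.75, rounded up to 15, and 15 + 5 = 20. Resectability class does not enter, so this point leaves the sample size alone.

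**What a resectable result at 6 months counts.**

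| Cohort | Resectable at baseline | A resectable result means |
|---|---|---|
| Section 9.1 | 0 of 20 | conversion only |
| Criterion 3.1.a | no number set | conversion, or resectable throughout |

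**Illustration of size.** The documents give no resectable share, conversion rate or AUC. Every input here is assumed:

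- f, share resectable at baseline: 0.10, 0.25 or 0.50 (2, 5 or 10 of 20)
- r, share of those still resectable at 6 months: 0.8 to 1.0
- c, conversion rate in the others: 0.2 to 0.4

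*Share of resectable results that are not conversions* = fr / (fr + (1 − f)c).

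- f = 0.10: 0.08/(0.08 + 0.36) = 18% to 0.10/(0.10 + 0.18) = 36%
- f = 0.25: 0.20/(0.20 + 0.30) = 40% to 0.25/(0.25 + 0.15) = 63%
- f = 0.50: 0.40/(0.40 + 0.20) = 67% to 0.50/(0.50 + 0.10) = 83%

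Other assumed rates (r 0.8 to 0.9, c 0.1 to 0.3) give 40% to 69% with 4 of 20 resectable at baseline (3.2/8.0 to 3.6/5.2), and 73% to 90% with 10 of 20 (8/11 to 9/10).

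*Pooled AUC.* Suppose FLT change separates converters from non-converters with AUC 0.80 and, in patients resectable at baseline, is unrelated to 6-month status. Let m be the share of those patients whose FLT change looks like a converter's. With h and g the converter-like shares among all positives and all negatives, the mixture formula reduces to

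AUC = 0.5 + 0.3(h − g), where h = (frm + (1 − f)c)/(fr + (1 − f)c) and g = f(1 − r)m/(1 − fr − (1 − f)c).

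- Lowest: f = 0.50, r = 1, c = 0.2, m = 0 gives h = 0.10/0.60 = 0.167 and g = 0, so AUC = 0.55.
- Highest: r = 1, m = 1 gives h = 1 and g = 0, so AUC = 0.80.
- With m set equal to c, the range is 0.596 to 0.763.

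**What is left if the conversion result is restricted to patients not resectable at baseline.** Expected conversions are 20(1 − f)c, from 20 × 0.5 × 0.2 = 2.0 to 20 × 0.9 × 0.4 = 7.2, or 1.5 to 5.4 if only 15 are evaluable. The Hanley-McNeil variance at AUC A, with p positives and n negatives, is [A(1 − A) + (p − 1)(A/(2 − A) − A²) + (n − 1)(2A²/(1 + A) − A²)]/(pn). At A = 0.80 the three bracketed terms are 0.16, 0.0267(p − 1) and 0.0711(n − 1).

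| Conversions | SE | 95% CI (upper limit capped at 1) |
|---|---|---|
| 2 of 10 | √(0.684/16) = 0.207 | 0.39 to 1.00 |
| 3 of 15 | √(0.996/36) = 0.166 | 0.47 to 1.00 |
| 7 of 18 | √(1.031/77) = 0.116 | 0.57 to 1.00 |

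**The case against.** **The sentence in 9.1 may be loose wording.** It states an expectation and is not an eligibility rule. With 3.1.b in mind it could mean patients not going straight to surgery, and 1.1 lists chemotherapy as initial treatment for resectable disease too. This stands in part: 3.1.b narrows the gap. It does not close it, because a patient with resectable disease who is a candidate for induction chemotherapy still qualifies.

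**The outcome is defined.** Sections 9.1 and 9.3 give an absolute status at 6 months, and predicting that status is a coherent aim. A reader might infer that conversion is the plan's stated target and that 9.3 fails to deliver it. The documents do not support this: conversion is suggested by 9.1 and by the goal in 1.1, but is nowhere declared. What stands is that 9.3 does not tell the reader which meaning applies, and the two cohorts give different ones.

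**Adjustment may deal with it.** The Study Summary lists cancer stage as a covariate. That sentence follows the Cox model for OS and PFS, and 9.3 does not carry it into the logistic model. Even if it did, adjustment would not change what the outcome counts.

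**The stakes are small.** Correct. The resectability analysis is in no objective and does not drive the sample size. The endpoint in 2.4 asks only whether a decrease "is related to longer progression free survival and overall survival".

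**Conclusion.** The contradiction is real and stands in current text. Its consequence is limited to the secondary 6-month analysis in 9.3: if resectable patients enrol, the pooled logistic model and AUC cannot be read as predicting who becomes resectable.

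The size is not known. Under the assumed rates, 18% to 83% of resectable results would not be conversions, and a conversion AUC of 0.80 would appear as 0.55 to 0.80, that is, from no distortion to a substantial one. The low end needs several extreme assumptions at once, and none of the inputs comes from the documents. The contradiction is certain; the amount of harm is not.

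A reader might also infer that the OS and PFS results have no clear population. The documents do not bear this out. Objectives 2.1 and 2.2 name all three disease classes, 3.1.a agrees, and Section 3.0 makes the criteria binding, so one outlying sentence in 9.1 does not unsettle the primary analysis.

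**What to change.** 1. Reconcile the population sentence in 9.1 with 3.1.a, so that the statistical section and the eligibility criteria describe the same cohort. Which cohort is intended is for the sponsor to decide.
2. If resectable patients remain eligible, record baseline resectability class as a data item. The Visit 1 list in Section 4.0 does not name it.
3. In 9.3, report the 6-month resectability result by baseline class. Take any statement about becoming resectable only from patients who were borderline resectable or locally advanced at baseline, with event counts and a 95% CI.

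The cost is wording in 9.1 and 9.3 plus one data item. The class must already be determined to apply 3.1.a, and staging imaging is part of Visit 1, so no new procedure is needed. The drawback is precision: the subset is smaller and, as the working shows, its interval may exclude little. That imprecision belongs in the report, since pooling the classes would answer a different question.

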## **9.2 Sample size**

The sample size was based on an ability to detect a relative group difference in FLT SUV (baseline versus interim) of 0.124 and standard deviation of 0.17. A sample size of 15 patients was calculated using a two-sided paired t test, power of 80 %, and the type I error rate was set to be 0.05. The expected response to therapy was assumed to be 20%.

Five patients were added to the sample size to compensate for dropout and no uptake on the baseline scan, leading to a total sample size of 20.

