Study Product(s), Dose, Route, Regimen	Fluorothymidine is an analog of the nucleoside thymidine (deoxythymidine) but the 3'-F atom prevents FLT from following the full biochemical pathway of thymidine. FLT is transported from the blood into cells by active transport; it does not freely diffuse across the cell membrane. Once in the cell, FLT is a substrate for thymidine kinase I (TK1) and is phosphorylated but is not incorporated into DNA. 5mCi of FLT (+/- 20%) will be given intravenously.
Duration of administration	IV push over one to two minutes
Reference therapy	Not applicable

Statistical Methodology	
The difference in SUVmax, SUVpeak and proliferative tumor volume between baseline and post 2 cycles of chemotherapy will be correlated with overall survival at 1 and 2 years (primary clinical outcome endpoint) and progression free survival at 6 months and at 1 year (secondary clinical outcome endpoint) of patients with resectable, borderline resectable or locally advanced pancreatic adenocarcinoma using univariate and multiple cox regression model. Patient demographic information and tumor and treatment characteristics such as sex, race, tumor grade, cancer stage, last treatment modality, will also be included. P value less than 0.05 will be considered as statistical significant.
 
Areas under the ROC curve (AUC) and corresponding 95% confidence interval will be calculated for all models. Leave one out cross validation will be applied to avoid over-fit.

-------------------------	---

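### The 80% power in section 9.2 is for mean FLT SUV change; the primary question, whether that change predicts survival by Cox regression, has no power or precision statement

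*Combined protocol and SAP*

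**What the plan says.** Section 9.2 bases the sample size on a "relative group difference in FLT SUV (baseline versus interim) of 0.124 and standard deviation of 0.17", and continues: "A sample size of 15 patients was calculated using a two-sided paired t test, power of 80" per cent, with a type I error rate of 0.05. Five patients are added for dropout and absent baseline uptake, giving 20. An expected response of 20% is mentioned but not tied to any survival quantity.

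The primary objective (2.1) is whether percentage change in the FLT parameters predicts overall survival (OS) at 1 and 2 years. Section 9.3 gives the primary outcome as the degree of change that "can predict patients overall survival and progression free survival", and the analysis as: "Univariate and multiple cox regression model are going to be used. P-value less than 0.05 will be considered as statistical significant". The synopsis repeats the Cox plan and the threshold: "P value less than 0.05 will be considered as statistical significant".

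Progression-free survival (PFS) has no settled rank. Section 2.4 puts it in the primary endpoint, that a PET response "is related to longer progression free survival and overall survival", and 9.3 does likewise. Section 2.2 and the synopsis call it secondary.

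**The concern.** A fall in mean SUV and an association between SUV change and survival are different hypotheses. Every patient's SUV could fall while the size of the fall said nothing about who lives longer. Power for the first is therefore not power for the second, and the only sample size justification in the plan belongs to a test that is not the primary analysis.

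What is at stake is how a non-significant Cox result will be read. The only stated rule for reading it is p<0.05. With at most 20 patients and no stated precision, p≥0.05 could mean that FLT change has no predictive value or that there were too few events to tell.

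**Working it through.** **1. The plan's own figure.** Inputs from 9.2: difference 0.124, SD 0.17, two-sided alpha 0.05, power 80%. Normal approximation, with z-values 1.960 + 0.842 = 2.8016:

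n = (0.17 × 2.8016 / 0.124)² = 14.75, rounded up to 15.

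So the 15 reproduces, and it contains no survival quantity.

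**2. Search for a survival justification.** The synopsis and sections 2.1, 2.2, 2.4, 4.1, 6.4.5, 9.1, 9.2 and 9.3 give no expected number of deaths or progressions, no survival rate, no target HR and no expected interval width.

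**3. What 20 patients can offer the primary question.** The plan supplies neither event counts nor an HR, so both are assumptions here and are shown over a range. For one standardised predictor, unadjusted, with D deaths and two-sided 0.05:

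- power ≈ Φ(ln HR × √D − 1.96), plus a negligible opposite tail
- HR detectable with 80% power = exp(2.8016/√D)
- best-case 95% CI = HR multiplied or divided by exp(1.96/√D)

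Example with D = 10 and HR 1.5: 0.4055 × 3.162 − 1.96 = −0.678, so power is 25%.

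| Deaths (assumed) | Power, HR 1.5 per SD | Power, HR 2.0 per SD | HR detectable at 80% | Best-case CI factor |
|---|---|---|---|---|
| 5 | 15% | 34% | 3.50 | 2.40 |
| 10 | 25% | 59% | 2.43 | 1.86 |
| 15 | 35% | 77% | 2.06 | 1.66 |
| 20 | 44% | 87% | 1.87 | 1.55 |

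The same figures apply to PFS at the same number of progression events.

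**4. Check by simulation.** The events formula is a large-sample result. Cox fits were simulated with 15 or 20 patients, exponential survival, a normally distributed predictor and Wald tests. Power for 10 to 20 deaths was about 20–34% at HR 1.5 and 43–71% at HR 2.0. At HR 1.5 the median CI factor was 2.0–2.1 at 10 deaths, 1.8–1.9 at 15 and 1.7 at 20. With 20 patients, an estimated HR of 1.5 would have a 95% CI of about 0.74 to 3.03 at 10 deaths (factor 2.02) or 0.87 to 2.58 at 20 deaths (factor 1.72).

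All of this is for a single predictor. The plan has three PET parameters, and the synopsis adds sex, race, grade, stage and last treatment modality, so the multiple Cox model would be less precise.

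**5. Minor point on the 15.** Section 9.2 names a t test, but 15 matches the normal approximation. If 0.124 and 0.17 are used untransformed (standardised difference 0.124/0.17 = 0.729), exact paired t power is 74.8% at 15, 80.6% at 17 and 87.1% at 20. If the analysis is of log ratios and 0.124 is a 12.4% decrease, the difference is −ln(0.876) = 0.1324. Taking 0.17 as the SD on that scale, the standardised difference is 0.1324/0.17 = 0.779, and power at 15 is 80.07%.

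**The case against.** The best defence is that this is a single-centre cohort titled an initial evaluation, with no go/no-go decision or treatment change attached to the Cox p-value. Formal power for survival is not required of such a study, and some estimation is already planned: "Areas under the ROC curve (AUC) and corresponding 95% confidence interval will be calculated for all models", with leave-one-out cross-validation. This largely stands as an argument against demanding a larger trial. It does not fill the gap. The AUC intervals are outputs without an expected width, no HR interval is planned, section 2.3 lists no exploratory objectives, and p<0.05 remains the stated criterion.

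Three stronger readings are tempting, and the documents do not support them.

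- A reader might infer that the survival analysis is bound to fail. That holds only for modest effects. At HR 2.0 per SD with 15 to 20 deaths, simulated power is about 52–71%, so detection is more likely than not. The plan gives no HR, so 1.5 cannot be treated as the expected effect.
- A reader might infer that the sample size of 15 is an arithmetic error. It reproduces by the normal approximation and may be right for the t test on a log scale.
- A reader might infer that 9.2 leaves the units of 0.124 and 0.17 wholly undefined. It says the difference is relative; only a possible log transformation is unstated.

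**Conclusion.** The concern holds as a mismatch between the stated power and the primary hypothesis, and should be fixed. The mismatch follows directly from 9.2 set against 2.1, 9.3 and the synopsis, and rests on no assumption. Its size does rest on assumptions: 5 to 20 deaths, an HR of 1.5 or 2.0 per SD, and one unadjusted predictor. Within that range, an HR near 1.5 would usually be missed, while an HR of 2.0 or more could be detected if most patients die. A non-significant Cox result would therefore not by itself show that FLT change lacks predictive value. The t-versus-normal difference is minor, conditional on the scale of analysis, and covered by the 20 enrolled if at least 17 are evaluable.

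**What to change.** - **Section 9.2:** state that the 80% power applies only to mean SUV change and not to the survival analyses. Give the expected deaths and progressions, over a range, with the resulting 95% CI width for the HR per SD. If a detectable HR is quoted, note that the events formula is optimistic with 15 to 20 patients.
- **Section 9.3 and the synopsis:** report each Cox result as an HR with its 95% CI, alongside the AUC intervals already planned, and say that p≥0.05 will not be read as no predictive value.
- **Section 9.2, minor:** say whether the SUV comparison is on untransformed relative change or log ratios. If untransformed, restate the power at 15 as 74.8% or the evaluable number as 17. If log ratios, the 80% at 15 stands.

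The cost is wording in three places, with no added patients, visits or scans. The downside is a less favourable stated claim for the primary analysis.

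### Section 9.2 states 80% power with 15 patients, but the paired t test it names has about 75% at 15 and reaches 80% only at 17 evaluable patients

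*Combined protocol and SAP*

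**What the plan says.** Section 9.2 (Sample size) gives the plan's only power calculation. Its inputs are a "relative group difference in FLT SUV (baseline versus interim) of 0.124 and standard deviation of 0.17", and "the type I error rate was set to be 0.05". The result is stated as "A sample size of 15 patients was calculated using a two-sided paired t test, power of 80" per cent. Enrolment is then raised from 15 to 20: "Five patients were added to the sample size to compensate for dropout and no uptake on the baseline scan". Between these statements stands "The expected response to therapy was assumed to be 20" per cent, with three references. The section does not say what this percentage measures or where it is used. It also does not say whether 0.17 is the standard deviation of the within-patient change or of a single scan.

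**The concern.** With 15 patients a paired t test has 14 degrees of freedom, and at that size the t and normal distributions differ enough to matter for power. A sample size that meets 80% only just under the normal formula will fall short under the t test. Because this is the only quantitative support for the size of the study, the stated power should be the power of the test that is named.

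The allowance for loss is tied to the same figure. If the test needs more than 15 evaluable patients, the margin of five is smaller than it appears. The 20% raises a separate question, because a reader cannot tell whether it is an input that was used, an input that was left out, or background.

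**Working it through.** **Inputs (all from section 9.2).** Difference 0.124; standard deviation 0.17; two-sided alpha 0.05; power 80%; 15 evaluable and 20 enrolled. Assumption: 0.17 is the standard deviation of the paired relative change. The text does not say so, but it is the natural reading for a paired test, and 15 reproduces under it.

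**Step 1: reproduce the plan's figure.** The standardised effect is 0.124/0.17 = 0.729. The normal-approximation formula is n = ((z₀.₉₇₅ + z₀.₈₀)/0.729)². With the numbers put in, n = (1.960 + 0.842)²/0.729² = 14.75, rounded up to 15. Normal-approximation power at 15 is Φ(0.729 × √15 − 1.960) = Φ(0.865) = 80.65%. Both the 15 and the 80% therefore follow from this formula.

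**Step 2: the test that is named.** For the two-sided paired t test, power is P(|T| > t₀.₉₇₅ with n − 1 degrees of freedom), where T is noncentral t with noncentrality 0.729 × √n. At n = 15 the noncentrality is 2.825.

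| Evaluable patients | Lost of 20 | Power, paired t test | Power, normal approximation |
|---|---|---|---|
| 15 | 5 (25%) | 74.8% | 80.65% |
| 16 | 4 (20%) | 77.8% | 83.1% |
| 17 | 3 (15%) | 80.6% | 85.3% |
| 18 | 2 (10%) | 83.0% | 87.2% |
| 20 | 0 | 87% | 90.4% |

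A simulation of 400,000 trials with n = 15 gave 74.9%.

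**Step 3: could rounding of the inputs explain the gap?** With the difference anywhere from 0.1235 to 0.1245 and the standard deviation from 0.165 to 0.175, t-test power at 15 runs from 72.0% to 77.6%. It does not reach 80%. For 80% at n = 15, the t test needs a difference of 0.132 (with SD 0.17) or a standard deviation of 0.159 (with difference 0.124).

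**Step 4: dependence on the meaning of 0.17.** If 0.17 were the standard deviation of a single scan, the standard deviation of the difference would be 0.17 × √(2(1 − ρ)), where ρ is the correlation between scans, which the plan does not give. Power at 15 would then be 46% at ρ = 0, 57% at 0.25, 75% at 0.5, 84% at 0.6 and 96% at 0.75.

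**Step 5: the 20%.** The calculation in step 1 yields 15 without it. It equals neither 0.124 nor 0.17.

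**The case against.** The strongest reply is that the plan's figures reproduce. A standard formula gives 15 and just over 80%, so this is a missing small-sample correction of two patients, not an invented number. That is fair as an explanation, and it rules out any inference that 15 has no basis in the stated inputs. It does not make the sentence correct, because the section says a t test was used and the t test does not have that power at 15.

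The second reply is that the consequence is small. This stands. Enrolment is 20, and power is at or above 80% with 17 or more evaluable. A reader might infer that the design cannot deliver 80%; the documents do not support that. The shortfall arises only if 4 or 5 of the 20 are lost, although a loss of 5 is what the plan allows for.

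Third, a reader might infer that the 20% contradicts the 12.4% difference, or that the study is larger than it needs to be. Either inference requires reading the 20% as a mean change in SUV. It could equally be a response rate or a threshold, and the section does not say. It is undefined, and no contradiction has been shown.

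Finally, no survival conclusion rests on this t test. Section 9.3 relates change in the PET parameters to overall and progression-free survival by Cox regression and names no paired t test; section 9.1 says only that the two scans will be compared. This also stands. Neither the 75% nor the 80% should be read as the power of the Cox analysis, for which the plan gives none.

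**Conclusion.** The stated power is wrong for the named test: 74.8% and not 80% at 15 evaluable patients, a gap of about 5 points. The test reaches 80% (80.6%) at 17. With 20 enrolled, the loss that can be absorbed while keeping 80% is 3 patients (15%), not 5 (25%). These figures rest on reading 0.17 as the standard deviation of the paired relative change; the arithmetic is otherwise firm and is not altered by rounding of the inputs. The 20% expected response plays no part in the calculation and is undefined. This is a misstatement worth correcting, with limited effect on the study, and it leaves the planned enrolment of 20 tenable.

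**What to change.** Restate section 9.2 in one of three equivalent ways, naming the exact paired t test as the method:

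- about 75% power with 15 evaluable patients for a difference of 0.124;
- 80% power with 15 evaluable patients for a difference of about 0.132;
- 80% power for 0.124 with 17 evaluable patients, allowing for the loss of at most 3 of 20 (15%).

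In each case, say that 0.17 is the standard deviation of the paired relative change, if that is what it is; if it is not, give the correlation assumed and recompute. Delete the 20% expected response, or say what it measures and how it was used. Add a sentence saying that this power refers to the baseline-to-interim change in SUV and not to the survival analyses in section 9.3.

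The cost is wording only, with no extra patients. The price is a slightly less favourable stated power, a slightly larger detectable difference or a smaller allowance for loss, depending on which version is chosen.
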